9.1. Adverse Events

Adverse events will be coded using the MedDRA coding thesaurus (version 21.0). All AEs recorded in the clinical database starting after the last visit on the VMDN-003 study will be considered a treatment-emergent adverse event (TEAE). All AE summary tables will include the number and percentage of subjects with an AE within a category, system organ class (SOC), and preferred term.

An overall summary of the number and percentage of subjects with TEAEs will be provided by treatment group. Frequencies and percentages of the following will be included: subjects with any TEAE, subjects with any TEAE leading to discontinuation, subjects with any TEAE leading to death, and subjects with any serious treatment-emergent AE (SAE).

The incidence of TEAEs will be summarized with frequencies and percentages by the following:

- SOC and PT
- SOC and PT by maximum severity
- SOC and PT by relationship to study medication
- SOC and PT by relationship to injection procedure.
- SAEs by SOC and PT
- AEs of special interest by SOC and PT

There are 4 types of AEs of special interest (AESI):

- Ophthalmological events that could potentially suggest causality related to HGF and its angiogenic potential
- Acute cardiac events

- Foot ulcers
- AEs related to pregabalin or gabapentin and their occurrence rates with in conjunction with VM202

Adverse event data will be summarized by treatment group and by treatment group within baseline gabapentin and pregabalin use.

All adverse events will be presented in a listing.

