5. EVALUATION OF ADVERSE EVENTS

5.1. **DEFINITIONS**

An Adverse Event (AE) is the development of an untoward medical occurrence or the deterioration of a pre-existing medical condition following or during exposure to an investigational product, whether or not considered causally related to the product.

An untoward medical condition can be symptoms (e.g., nausea, chest pain), signs (e.g., tachycardia, enlarged liver) or clinically significant abnormal results of an investigation (e.g., laboratory findings, electrocardiogram).

Conditions or diseases that are chronic but stable should not be recorded as an AE. Changes in a chronic condition or disease that are consistent with natural disease progression are NOT considered AEs and also should not be recorded on AE worksheets. These medical conditions should be adequately documented on the appropriate page of the study worksheet (relevant medical history and/or physical examination). However, medical conditions present at enrollment that worsen in intensity or frequency in a manner inconsistent with the natural course of the disease during the treatment or post-treatment periods should be reported and recorded as AEs.

An adverse reaction means any adverse event caused by a drug. Adverse reactions are a subset of all suspected adverse reactions for which there is reason to conclude that the drug caused the event.

Suspected adverse reaction means any adverse event for which there is a reasonable possibility that the drug caused the adverse event. For the purposes of IND safety reporting, 'reasonable possibility' means there is evidence to suggest a causal relationship between the drug and the adverse event. A suspected adverse reaction implies a lesser degree of certainty about causality than adverse reaction, which means any adverse event caused by a drug.

A serious adverse event (SAE) is any untoward medical occurrence which:

- Results in death:
- Is life-threatening;
- Requires inpatient hospitalization (admission to hospital with a stay > 24 hours) or prolongation of hospitalization which is not specifically required by the protocol or is elective;
- Results in permanent impairment of a body function or permanent damage to a body structure; or
- Requires medical or surgical intervention to preclude permanent impairment of a body function or permanent damage to a body structure.

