5.6. STUDY ENDPOINTS

5.6.1. PRIMARY ENDPOINTS

The primary endpoint is the difference in long-term safety – defined as occurrence of adverse events - observed between subjects receiving VM202 versus subjects receiving placebo in the VMDN-003 study.

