2.2. Study Endpoints

2.2.1. Safety Endpoints

The primary endpoint is the difference in long-term safety – defined as occurrence of adverse events – observed between subjects receiving VM202 versus subjects receiving placebo in the VMDN-003 study.

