6.1.7. Derived Variables

- The Average 24-hour Pain Score will be derived by taking the average of the daily pain
 measurements recorded by a subject prior to a visit. The score will only be derived if a
 subject completes at least 5 of 7 days of diary entries within the 14 days prior to the visit.
- The Average 24-hour Sleep Interference Score will be derived by taking the average of the daily sleep interference measurements recorded by a subject prior to a visit. The score will only be derived if a subject completes at least 5 of 7 days of diary entries within the 14 days prior to the visit.
- Change from baseline = value at current time point value at baseline.
- Treatment-Emergent Adverse Event (TEAE) = All adverse events collected in the VMDN-003b clinical database with a start date after the last visit on the VMDN-003 study will be considered treatment-emergent.

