Note: The denominator for percentage corresponds to the N in each column. N is the number of subjects in the safety population. Subjects are summarized by treatment received in the VMDN-003 study.

[1] P-value from a Cochran-Mantel-Haenszel (CMH) test (stratified by baseline use of gabapentin/pregabalin) comparing VM202 to Placebo. SOURCE: Listing 16.2.6.2

[figure not shown]
[figure not shown]

Table 14.2.5.2
Summary of Patient's Global Impression of Change (PGIC) by Gabapentin and/or Pregabalin use at Baseline mITT Population

Same shell as Table 14.2.5.1, add a row at the top of table reading "Group: Gabapentin and/or Pregabalin Use". Once all records from group are summarized, update row text to "Group: No Gabapentin and/or Pregabalin Use" and start table on a new page. Do not include the CMH test or footnote.

Helixmith Co., Ltd. Protocol VMDN-003b

CONFIDENTIAL

Page x of y <Version>

Table 14.3.1.1.1 Summary of Treatment Emergent Adverse Events Safety Population

Category	Placebo (N=XX) n (%)	VM202 (N=XX) n (%)	Overall (N=XX) n (%)
Subjects with at least one TEAE	XX (XX.X%)	XX (XX.X%)	XX (XX.X%)
Subjects with at least one TEAE related to study medication	XX (XX.X%)	XX (XX.X%)	XX (XX.X%)
Subjects with at least one TEAE related to injection procedure	XX (XX.X%)	XX (XX.X%)	XX (XX.X%)
Subjects with at least one TEAE leading to discontinuation	XX (XX.X%)	XX (XX.X%)	XX (XX.X%)
Subjects with at least one TEAE leading to death	XX (XX.X%)	XX (XX.X%)	XX (XX.X%)
Subjects with at least one SAE	XX (XX.X%)	XX (XX.X%)	XX (XX.X%)

Abbreviations: PT = Preferred Term; SOC = System Organ Class; TEAE = Treatment emergent adverse event; SAE = Serious treatment emergent adverse event; N = Number of subjects in the safety population; n = Number of subjects with events.

Note: The denominator for percentage corresponds to the N in each column. Subjects are summarized by treatment received in the VMDN-003 study. AEs were coded using MedDRA version 21.0. A TEAE is any AE that occurs after the last visit in the VMDN-003 study and pre-existing medical conditions that worsen following the last visit in the VMDN-003 study.

SOURCE: Listing 16.2.7.1

[figure not shown]
[figure not shown]

Table 14.3.1.1.2

Summary of Treatment Emergent Adverse Events by Gabapentin and/or Pregabalin use at Baseline Safety Population

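### The SAP text defines a treatment-emergent adverse event by start date alone, while the notes on the AE tables also count pre-existing conditions that worsen

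*SAP*

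**What the plan says.** The primary endpoint has the same wording in both documents. Protocol 5.6.1 begins "The primary endpoint is the difference in long-term safety", defined as the occurrence of adverse events, and SAP 2.2.1 compares what is "observed between subjects receiving VM202 versus subjects receiving placebo in the VMDN-003 study". Neither uses the term TEAE. That term enters through SAP 9.1, which builds the incidence summaries on TEAEs.

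The SAP defines the term in two ways:

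- **Start date only.** Section 6.1.7 takes events in the "VMDN-003b clinical database with a start date after the last visit on the VMDN-003 study". Section 9.1 counts recorded events "starting after the last visit on the VMDN-003 study will be considered a treatment-emergent adverse event (TEAE". Neither mentions worsening.
- **Start date or worsening.** The notes to Tables 14.3.1.1.1, 14.3.1.2.1, 14.3.1.3.1 and 14.3.1.4.1 count events occurring after the last VMDN-003 visit "and pre-existing medical conditions that worsen following the last visit in the VMDN-003 study".

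Protocol 5.1 requires medical conditions present at enrollment to be recorded as AEs when they "worsen in intensity or frequency in a manner inconsistent with the natural course of the disease". It does not say which onset date to enter. It also excludes changes that fit natural disease progression.

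**The concern.** The extension exists to look at safety beyond Day 270, and the TEAE tables are where the two arms are compared. If Section 6.1.7 is programmed as written, the printed notes will claim a rule that was not applied. If the notes are programmed, the output departs from the formal derivation, and no SAP text says how worsening is to be found.

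The events at risk are those that began before the extension window and became more severe, more frequent or serious within it. A foot ulcer that starts during VMDN-003 and becomes serious after Day 270 is an example. If its record keeps the earlier onset date, it would be missing from both the serious TEAE tables and the special-interest tables, whose shells are titled for serious TEAEs.

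**Working it through.** No formula in the plan applies, and the plan gives no figure to reproduce. The check sets the definitions side by side and applies each to test cases.

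**Reach of the notes.** Four shells carry the worsening clause. Ten more tables are specified as the same shell as one of these four: 14.3.1.1.2, 14.3.1.2.2, 14.3.1.3.2, 14.3.1.4.2, 14.3.1.5.1, 14.3.1.5.2, 14.3.2.1.1, 14.3.2.1.2, 14.3.3.1.1 and 14.3.3.1.2. That makes 4 + 10 = 14, which is every AE summary table in the SAP.

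**Test cases.** Take the last VMDN-003 visit as Day 270. The other days are illustrative.

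| Case | How it is recorded | Start-date rule (6.1.7, 9.1) | Table notes |
|---|---|---|---|
| (a) AE with onset Day 200, worsens Day 300 | One record, onset Day 200 | Not a TEAE | TEAE |
| (b) Medical-history condition worsens Day 300 | New AE record, onset Day 300 | TEAE | TEAE |
| (c) New AE on Day 300 | New AE record, onset Day 300 | TEAE | TEAE |

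The rules disagree only in case (a), where a worsened condition keeps an onset date on or before the last VMDN-003 visit.

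**Can case (a) arise?** The documents leave it open:

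- Protocol 5.3 runs AE collection without a break from Day 0 to the Day 365 visit.
- Protocol 5.2 has every AE followed until it resolves or stabilises.
- Listing 16.2.7.1 shows one onset date and the worst intensity per event, with no date of worsening.
- No passage says whether worsening opens a new record.

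**Effect on the counts.** In one arm, let p be the proportion of subjects with a new-onset event. Let w be the proportion of the remaining subjects who have a case (a) event. The start-date rule gives p and the notes give p + w(1 − p), so the notes can never give the lower incidence. For the difference between arms the shift is w₁(1 − p₁) − w₀(1 − p₀), with 1 for VM202 and 0 for placebo, and this can have either sign. The documents supply neither p nor w, and SAP 3.2 states no sample size.

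Subjects are counted once per row. A subject who also has a new-onset event leaves the any-TEAE row unchanged but can still change the preferred-term, maximum-severity and serious-event rows.

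**The case against.** The strongest reply is that Protocol 5.1 treats worsening as an AE in its own right. If sites enter it as a new record dated at the worsening, both rules count it and the notes are true. That is a natural reading, and it stands to this extent: the loss is conditional. A reader might infer that the derivation drops all worsening events, but the documents do not show that.

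Other limits also stand:

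- A reader might say that the primary endpoint itself has two definitions. It does not; only the term used to tabulate it does.
- Which rule will be programmed is not settled. Section 6.1.7 is the formal derivation, but SAP Section 13 also calls the shells programming guidance.
- It is tempting to argue that all the special-interest classes begin early and progress. Acute cardiac events have their own onset, and progression along the natural course is not recorded as an AE. Effects that first appear after Day 270 are counted under both rules.
- Affected events remain visible. All AEs are listed, and the DSMB reviews all reported AEs. But a listing does not correct a by-arm incidence.

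It could also be said that the notes can simply be edited, since Section 13 lets footnotes change without a SAP modification. That argues for acting now. The provision covers minor, cosmetic changes, whereas this choice decides which events count. It belongs in a plan that the SAP Overview describes as set before any unblinded analysis.

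**Conclusion.** The inconsistency is real and should be corrected before the AE tables are programmed. Two stated rules give different counts for one identifiable kind of event, in all the tables that report the primary safety outcome. The size is unknown: with no AE rates or numbers of carried-over events in the documents, any percentage would be invented. The conclusion rests on two assumptions. One is that at least some worsened conditions keep their earlier onset date, which the documents neither require nor prevent. The other is that becoming serious counts as worsening under the notes. If every worsening is entered as a new record with its own date, the two rules agree and only the wording needs aligning.

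**What to change.** Use one definition in Sections 6.1.7 and 9.1 and in all AE table notes: a TEAE is an AE with onset after the last VMDN-003 visit, or a pre-existing condition or AE that worsens in intensity, frequency or seriousness after that visit, consistent with Protocol 5.1. Intensity and frequency are the protocol's own criteria; seriousness is added so that the serious-event tables follow the same rule. Carry over the protocol's exclusion of natural disease progression, which the current notes omit.

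Then state how worsening is identified. Either it is recorded as a new AE dated at the worsening or, where the earlier record is carried over, the VMDN-003b record is compared with the VMDN-003 AE record for the same subject.

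The cost is SAP wording and a small amount of derivation work linking the two AE datasets. Protocol 3.4.2 keeps the same subject identifier across the studies, and the SAP already uses VMDN-003 data for baseline and earlier visits. Check one thing first: the comparison needs intensity, frequency and seriousness to be held in comparable form in both datasets, and the VMDN-003 dataset structure is not shown here.

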9.1.1. Adverse Events Leading to Withdrawal

A data listing of AEs leading to withdrawal of study drug will also be provided, displaying details of the event(s) captured on the CRF.

9.1.2. Deaths and Serious Adverse Events

Any deaths that occur during the study will be listed.

9.2. Vital Signs

Descriptive summaries of actual values and changes from baseline will be calculated for systolic blood pressure, diastolic blood pressure, weight, heart rate, respiration rate, temperature, and body mass index (BMI).

The height collected in the VMDN-003 study will be used to derive the BMI at the Day 365 visit based on the weight collected at the Day 365 visit.

Vital signs data will be summarized by treatment group and by treatment group within baseline gabapentin and pregabalin use.

All vital signs data will be listed.

9.3. Concomitant Medication

Concomitant medications will be coded using the World Health Organization Drug Dictionary Enhanced (WHO-DDE) (Version March 01, 2018 or later) thesaurus.

[figure not shown]
Frequencies and percentages of subjects taking concomitant medications will be presented by anatomic therapeutic class (ATC) level 3 and preferred base name. Concomitant medication data will be summarized by treatment group and by treatment group within baseline gabapentin and pregabalin use.

A medication will be considered concomitant if the subject started taking it after the last visit on the VMDN-003 study. Subjects will be counted once for each ATC and PT.

All medications will be listed.

10. Changes from Planned Analysis

Not applicable.

11. Other Planned Analysis

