4. EXAMINATIONS AND EVALUATIONS

4.1. CONCOMITANT MEDICATIONS

All concomitant medications (taken since completion of Day 270 of the VMDN-003 study) will be recorded at each study visit. For each medication taken, the following information will be collected:

- Medication trade name;
- Indication for which the medication was given;
- Dose/strength, route, and frequency of administration;
- Date started and date stopped (or continuation at study exit).

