 - If the year matches the year of first dose date and the end date (if present) is after first dose date, or AE is ongoing, then impute as the month and day of the first dose date.
 - If the year of AE onset < year of initiation of the treatment, then the month and day will be set to December 31st.
 - If the year of AE onset > the year of initiation of treatment, then the month and day will be set to January 1st.
- When the year and day are present and the month is missing:
 - If the year of AE onset = the year of initiation of the treatment, then the month will be set to the month of initiation of the treatment.
 - o If the year of AE onset < the year of initiation of the treatment, then the month will be set to December.
- If the year and month are known, but the day is unknown, then:
 - o If the year of AE onset = the year of initiation of the treatment and:
 - the month of AE onset = the month of initiation of the treatment, then the day will be set to the day of initiation of the treatment.
 - the month of AE onset < the month of initiation of the treatment, then the day will be set to the last day of month.

- if the month of AE onset > the month of initiation of the treatment, then the day will be set to the 1st day of month.
- If the year of AE onset < the year of initiation of the treatment, then the day will be set to the last day of month.
- If the year of AE onset > the year of initiation of the treatment, then the day will be set to the 1st day of month.

If the imputed AE onset date is after the AE stop date, then the onset date will be set to the stop date.

If an AE has a missing severity, it will be considered severe. If an AE has a missing relationship to study medication, injection procedure, or underlying disease, it will be considered related.

Baseline gabapentin/pregabalin use will be set based on the baseline gabapentin/pregabalin use from the VMDN-003 study.

7. Study Patients/Subjects and Demographics

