8.2. Daily Pain Diary Subgroup Analysis

The daily pain diary data will be analyzed within the below subgroups:

- Baseline HbA1c (< and ≥ median)
- Gender (male and female)
- Age (<65 years and > 65 years).

For baseline HbA1c, the median will be the VMDN-003 median and subjects will be summarized within the same group as that study. For each subgroup of the ITT population, the

change in average 24-hour pain score will be summarized by treatment group and visit using descriptive statistics including mean, median, standard deviation, minimum, and maximum. The count and percentage of subjects with a change in the average 24-hour pain score will also be summarized by treatment group and visit for each subgroup of the ITT population. Both types of descriptive summaries are also provided for the subgroups of baseline use of gabapentin and/or pregabalin, study center, and VMDN-003 protocol version the subject enrolled under.

Except for the subgroups of study center and protocol version, the Repeated Measures Model analyses described in Section 8.1 will be performed within each subgroup.

A sensitivity analysis excluding subjects that took prohibited medications on more than 14 consecutive days will be presented also. Both types of descriptive summary statistics and efficacy models will be run with these subjects excluded.

Additionally, the possible treatment-by-subgroup interaction will be tested for each subgroup variable as follows:

- A subgroup variable will be included in the primary analysis models described in Section 8.1 along with its interaction with the treatment effect. If the p-value of the interaction term is ≥ 0.05, the treatment-by-subgroup interaction is not significant.
- If the interaction effect is statistically significant (i.e., p-value < 0.05), then the Gail and Simon test will be used to test for the qualitative interaction at a significance level of 0.05 and provided as an aid for interpretation.

The Repeated Measures Model analyses described in Section 8.1 already accounts for the subgroups of baseline use of gabapentin and/or pregabalin (i.e., Yes and No groups). For evaluating the interaction between treatment and baseline use of gabapentin and/or pregabalin, the interaction effect will be added to the primary analysis models. If the interaction effect is significant, then the Gail and Simon test will be used to test for the qualitative interaction at a significance level of 0.05.

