Abbreviations: CFB = change from baseline.

Note: N is the number of subjects in the safety population. Subjects are summarized by treatment received in the VMDN-003 study.

[1] The baseline value for each variable is the value recorded at the last visit on or before start of dosing in the VMDN-003 study.

SOURCE: Listing 16.2.8

AD-ST-33.05 Effective date: 22-Jan-2018

[figure not shown]

Figure 2 (continued)

Table 14.3.6.2 Summary of Vital Signs by Gabapentin and/or Pregabalin Use at Baseline Safety Population

Same shell as Table 14.3.3.1, add a row at the top of table reading "Group: Gabapentin and/or Pregabalin Use". Once all records from group are summarized, update row text to "Group: No Gabapentin and/or Pregabalin Use" and start table on a new page.

[figure not shown]

Figure 2 (continued)

Helixmith Co., Ltd. Protocol VMDN-003 / E

CONFIDENTIAL

Page x of y <Version>

Table 14.3.7.1 Summary of Concomitant Medications by ATC Class Level 3 and Preferred Base Name Safety Population

Anatomical Therapeutic Chemical Preferred Base Name	Placebo (N=XX) n (%)	VM202 (N=XX) n (%)	Overall (N=XX) n (%)
Subjects with at least 1 Concomitant Medication	XX (XX.X%)	XX (XX.X%)	XX (XX.X%)
ATC Class 1	XX (XX.X%)	XX (XX.X%)	XX (XX.X%)
Preferred Base Name 1	XX (XX.X%)	XX (XX.X%)	XX (XX.X%)
Preferred Base Name 2	XX (XX.X%)	XX (XX.X%)	XX (XX.X%)
Preferred Base Name 3	XX (XX.X%)	XX (XX.X%)	XX (XX.X%)
ATC Class 2	XX (XX.X%)	XX (XX.X%)	XX (XX.X%)
Preferred Base Name 1	XX (XX.X%)	XX (XX.X%)	XX (XX.X%)
Preferred Base Name 2	XX (XX.X%)	XX (XX.X%)	XX (XX.X%)
Preferred Base Name 3	XX (XX.X%)	XX (XX.X%)	XX (XX.X%)

Abbreviations: ATC = Anatomical therapeutic chemical

Note: The denominator for percentage corresponds to the N in each column. N is the number of subjects in the safety population. Subjects are summarized by treatment received in the VMDN-003 study. Medications were coded using WHO-DDE version March 2018. Concomitant medications are all medications that started after the last visit on the VMDN-003 study. A medication with a missing start date and a stop date that is either missing or on or after the treatment start date will be considered as concomitant. Medications are displayed by descending frequency of Anatomical Therapeutic Chemical (ATC) Level 3 classification, by preferred base name within ATC, and then alphabetically. Subjects were counted only once for each ATC class and preferred base name. SOURCE: Listing 16.2.9

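### SAP 9.3 defines concomitant medication by start date, so drugs continued from VMDN-003 are collected but left out of Tables 14.3.7.1 and 14.3.7.2

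*SAP*

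**What the plan says.** SAP 9.3 gives the definition: "A medication will be considered concomitant if the subject started taking it after the last visit on the VMDN-003 study". The note to Table 14.3.7.1 repeats it: "Concomitant medications are all medications that started after the last visit on the VMDN-003 study". The note then makes one exception, for this case: "A medication with a missing start date and a stop date that is either missing or on or after the treatment start date". Treatment start here is the first dose in VMDN-003 (SAP 6.1.8). Table 14.3.7.2 gives the same summary within the gabapentin/pregabalin strata. Its shell refers to a Table 14.3.4.1 that is not among the planned tables; I take Table 14.3.7.1 to be meant.

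The protocol goes by use, not by start. Section 4.1 reads: "All concomitant medications (taken since completion of Day 270 of the VMDN-003 study) will be recorded at each study visit". It asks for start date and for stop date or continuation at exit, so continuing drugs are in the database with their dates.

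Three other provisions bear on background treatment:

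- SAP 9.3 also says: "All medications will be listed". Listing 16.2.9.2 does this, with start, end and ongoing status.
- SAP 6.1.8 fixes the strata: "Baseline gabapentin/pregabalin use will be set based on the baseline gabapentin/pregabalin use from the VMDN-003 study".
- SAP 8.2 adds: "A sensitivity analysis excluding subjects that took prohibited medications on more than 14 consecutive days will be presented also".

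SAP 10 records no change from the planned analysis, so the move from use to start date is not flagged.

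**The concern.** Durability of efficacy is a stated objective and is read from the Day 365 diary. The extension is non-interventional, and its only medication restriction is the exclusion for current use of an investigational drug or treatment. Anyone interpreting Day 365 pain by arm will want to know what each arm was taking at that time, and Tables 14.3.7.1 and 14.3.7.2 are where they will look.

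Under the start-date rule those tables describe only drugs begun in the extension interval. A subject whose medicines are all long-standing, with documented start dates, counts as having no concomitant medication. A subject who began pregabalin at Day 200 and still takes it at Day 365 counts as not taking it.

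Actual use in this period also helps in reading the fourth event of special interest, "AEs related to pregabalin or gabapentin and their occurrence rates with in conjunction with VM202". That link is indirect: the planned tables for those events count adverse events, split by baseline use, and do not rely on the SAP 9.3 definition.

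**Working it through.** The documents state no figure on this point, so there is nothing to reproduce. The check applies both rules to example records and then sizes the gap under stated assumptions.

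**Interval covered.** With nominal Day 270 as the last VMDN-003 visit, the table captures only starts within 365 − 270 = 95 days, or 81 to 109 days with the ±14-day window.

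**Classification.** Assumed dates: Day 0 is 15 Jan 2018, so Day 270 is 12 Oct 2018. Partial start dates are imputed by SAP 6.1.8.

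| Record | Start used | SAP 9.3 and table note | Taken since Day 270 |
|---|---|---|---|
| Gabapentin since 2015, ongoing | as recorded | no | yes |
| Analgesic from Day 100, ongoing | as recorded | no | yes |
| Analgesic from Day 300, full date | as recorded | yes | yes |
| Start wholly missing, ongoing | missing | yes | yes |
| Began Nov 2018, only year known, ongoing | 15 Jan 2018 | no | yes |
| Began 20 Oct 2018, day unknown, ongoing | 1 Oct 2018 | no | yes |

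Rows 1 and 2 are the main defect. Rows 1 and 4 together show an anomaly: a continuing drug enters the table if its start is unknown and leaves it once the start is documented. Rows 5 and 6 are true new starts that drop out because the imputation is keyed to first dose, or defaults to the first of the month, while the cut-off is the last VMDN-003 visit.

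**Size.** Let c be the share of an arm continuing a drug class with a known start on or before the last VMDN-003 visit, and n the share of the remainder who start it afterwards.

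- True use = c + (1 − c)n
- Displayed use = (1 − c)n
- Shortfall = c

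| c | n | True use | Displayed |
|---|---|---|---|
| 30% | 2% | 31.4% | 1.4% |
| 30% | 5% | 33.5% | 3.5% |
| 30% | 10% | 37.0% | 7.0% |
| 50% | 2% | 51.0% | 1.0% |
| 50% | 5% | 52.5% | 2.5% |
| 50% | 10% | 55.0% | 5.0% |
| 70% | 2% | 70.6% | 0.6% |
| 70% | 5% | 71.5% | 1.5% |
| 70% | 10% | 73.0% | 3.0% |

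True use runs from 31.4% to 73.0% and displayed use from 0.6% to 7.0%. The extremes of the two ranges fall in different rows; within each row the gap is c.

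A difference between arms in c is also hidden. Purely as an illustration, put one arm at c = 30% and the other at c = 50%, both with n = 5%. True use is 33.5% against 52.5%, a difference of 19.0 points. The table shows 3.5% against 2.5%, a difference of 1.0 point in the opposite direction.

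**Whether another table fills the gap.** The strata and Table 14.1.2.1 show gabapentinoid use at VMDN-003 baseline, so drugs added between Day 0 and Day 270 are missed. The prohibited-medication analyses (Tables 14.2.1.5.1–2, 14.2.1.6.1–2 and 14.2.2.6) rerun the pain results with exclusions but do not report use by arm, and neither document lists the prohibited drugs. That leaves the listing.

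**The case against.** The case against a strong reading is good on several counts.

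- *The data are not lost.* Every medication is listed with its dates under a treatment-received header. This stands, but a subject-level listing is not a summary by arm.
- *Not every long-standing drug is dropped.* If the start year is unknown, SAP 6.1.8 leaves the date missing, and the table note then counts the drug when its stop date is missing or falls on or after treatment start. This stands; the omission is of drugs with a known or imputed start on or before the last VMDN-003 visit.
- *The plan does address added medication.* The sensitivity analysis in SAP 8.2 covers both descriptive summaries and models, and baseline gabapentinoid use is a term in the efficacy models. This stands as indirect protection, with the limits noted above.
- *The VMDN-003 protocol is not to hand.* What was allowed or tabulated before Day 270 cannot be judged here. This stands, and it is why no usage rate can be asserted.
- *Concomitant medication is not an endpoint.* True; the effect is on two descriptive tables and on how the efficacy results are read.

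A reader might also infer that a drug with unknown start that stopped on Day 30 would be counted. The note's wording would admit it, but protocol 4.1 collects only drugs taken since Day 270, so it should not reach the table. What remains is that the exception is keyed to the wrong date.

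**Conclusion.** The definition conflicts with protocol 4.1 and should be corrected. As written, drugs with a known start on or before the last VMDN-003 visit and still in use are omitted from Tables 14.3.7.1 and 14.3.7.2, and the row counting subjects with any concomitant medication is understated. The shortfall for a drug class equals the share of subjects continuing it: 30 to 70 points under the assumed range. That range is illustrative, since the documents give no rates, and it takes all continuing users to have a known start date.

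Two stronger inferences are not supported. One is that the tables would show no use at all in either arm while a real imbalance exists. That needs no new starts after Day 270, no missing start dates, and rates the documents do not give. The other is that a corrected table would settle whether Day 365 pain relief is due to background treatment. It is an incidence count in the safety population by treatment received, without dose or change over time, while efficacy is analysed by randomized treatment. It could reveal an imbalance between arms, but it could not attribute pain relief to that imbalance.

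**What to change.** In SAP 9.3 and the notes to Tables 14.3.7.1 and 14.3.7.2:

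1. Define a medication as concomitant if it was taken on any day after the last VMDN-003 visit, that is, if it is ongoing or its stop date is missing or after that visit, whatever the start date.
2. Flag each medication as newly started after that visit or continuing from before it, and show the two separately.
3. Key the missing-start-date exception to the last VMDN-003 visit instead of treatment start.
4. For the new-or-continuing flag, anchor partial-start-date imputation to that visit instead of first dose. State how a partial date compatible with either side is classed: imputing to the visit date itself would still fail a strict test of starting after the visit.
5. Record the definition in SAP 10 if any departure from protocol 4.1 is kept.

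The cost is SAP wording, minor reprogramming and a longer table. Start, stop and ongoing status are already collected, so no new data are needed.
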